4.3.3 Investigational Medicinal Product Accountability

Emicizumab, the only IMP in Study YO39309, is required for completion of this study and will be provided by the Sponsor, and accountability for each vial is required throughout the study. The study site will acknowledge receipt of IMPs using the interactive voice or web-based response system (IxRS) to confirm the shipment condition and content. Any damaged shipments will be replaced. The investigator or designee must confirm that appropriate temperature conditions have been maintained during transit, either by time monitoring (shipment arrival date and time) or temperature monitoring, for all IMP received and that any discrepancies have been reported and resolved before use of the IMPs. All IMPs must be stored in a secure, environmentally controlled, and monitored (manual or automated) area in accordance with the labeled storage conditions, with access limited to the investigator and authorized staff.

Used and unused IMP vials will be returned by study patients to the site and appropriately accounted for. Used vials will then be disposed of at the study site according to the study site's institutional standard operating procedure. Instructions regarding how to handle unused vials should be obtained from the Sponsor. The site's method of IMP destruction must be agreed to by the Sponsor. The site must obtain written authorization from the Sponsor before any IMP is destroyed, and IMP destruction must be documented on the appropriate form.

Accurate records of all IMPs received at, dispensed from, returned to, and disposed of by the study site should be recorded on the Drug Inventory Log.

4.3.4 Post-Trial Access to Emicizumab

The Sponsor will offer post-trial access to the study drug (emicizumab) free of charge to eligible patients in accordance with the Roche Global Policy on Continued Access to Investigational Medicinal Product, as outlined below.

A patient will be eligible to receive study drug after completing the study if all of the following conditions are met:

- The patient has a life-threatening or severe medical condition and requires continued study drug treatment for his or her well-being
- There are no appropriate alternative treatments available to the patient
- The patient and his or her doctor comply with and satisfy any legal or regulatory requirements that apply to them

A patient will not be eligible to receive study drug after completing the study if any of the following conditions are met:

- The patient is eligible and has access to a study providing access to the drug
- The study drug is commercially marketed in the patient's country and is reasonably accessible to the patient (e.g., is covered by the patient's insurance or wouldn't otherwise create a financial hardship for the patient)
- The Sponsor has discontinued development of the study drug or data suggest that the study drug is not effective for hemophilia A
- The Sponsor has reasonable safety concerns regarding the study drug as treatment for hemophilia A
- Provision of study drug is not permitted under the laws and regulations of the patient's country

The Roche Global Policy on Continued Access to Investigational Medicinal Product is available at the following Web site:

http://www.roche.com/policy_continued_access_to_investigational_medicines.pdf

4.4 CONCOMITANT AND RESCUE THERAPY

Concomitant therapy includes any medication (e.g., prescription drugs, over-the-counter drugs, herbal or homeopathic remedies, nutritional supplements) used by a patient from 4 weeks prior to screening to the study completion/discontinuation visit. In addition, use of long-acting medications taken infrequently (e.g., zoledronic acid, denosumab) will be recorded as well. All such medications should be reported to the investigator and recorded on the Concomitant Medications eCRF.

4.4.1 Permitted Therapy

Concomitant use of the following drugs and therapies will be permitted:

- Drugs intended to control bleeds, including FVIII products or bypassing agents as standard-of-care episodic treatment. Exact dosages will not be specified in the study; however, investigators should consider that circulating emicizumab may increase patients' coagulation potential. Investigators should review with patients the dose to be used to treat breakthrough bleeds. Breakthrough bleeds should be treated with the lowest FVIII or rFVIIa dose expected to achieve hemostasis, which may be lower than the patients' prior FVIII or rFVIIa dose.

Caution should be taken for patients who are using rFVIIa (e.g., consideration of using no more than 90 µg/kg of rFVIIa as an initial dose).

Use of aPCC/PCC in combination with emicizumab should be avoided completely in patients who have the option of using other bypassing agents to treat bleeds. In the event that aPCC/PCC is the only available bypassing agent, the lowest dose expected to achieve hemostasis should be prescribed, with no more than 50 units/kg of aPCC/PCC to be administered as an initial dose.

Other bypassing agents (e.g., Byclot[®]) should be avoided. In cases where such agents are the only available bypassing agent, the lowest dose expected to achieve hemostasis should be prescribed, with no more than the lowest dose described in the prescribing information to be administered as an initial dose (e.g., no more than 60 µg/kg of Byclot[®]).

Exact dose and schedule of bypassing agents should be discussed with patients at the beginning and throughout the study. Repeated dosing of rFVIIa, aPCC/PCC, or other bypassing agents should be performed only under medical supervision, which includes laboratory monitoring by additional local laboratory assessments (see [Appendix 1-A](#)), and consideration should be given to verifying bleeds prior to repeated dosing.

Caution should be taken if anti-fibrinolitics are used in conjunction with rFVIIa in patients receiving emicizumab.

- Drugs and therapies to treat adverse events and use of topical antiseptics, anesthetics, eye drops, etc., that are not considered to result in systemic exposure
- Drugs to treat an existing medical condition ongoing at study entry that do not violate the eligibility criteria (e.g., anti-retroviral therapy for HIV infections)
- Local anesthetic cream for emicizumab SC administration
- Vaccinations should be administered following national immunization schedules. As per the World Federation of Hemophilia recommendations for vaccinations (World Federation of Hemophilia 2012), patients with hemophilia should be vaccinated. Thus, vaccinations should be administered according to the World Federation of Hemophilia recommendations and local Hemophilia Treating Center practice and ideally during a period when the bleeding status of the child is well controlled and stable. Vaccinations should not be administered on the same day as an emicizumab administration but ideally at a timepoint between two emicizumab administrations (>48 hours after emicizumab administration). Children who receive vaccinations must be carefully followed for any adverse reactions in the subsequent days following vaccine administration.

4.4.2 Prohibited Therapy

Use of the following therapies is prohibited during the study and for at least 4 weeks prior to initiation of study treatment:

- Drugs that would affect hemostasis (e.g., aspirin, non-steroidal anti-inflammatory drugs that are not selective or preferential cyclooxygenase-2 inhibitors, or anticoagulants [other than to flush, dwell, or de-clot a venous access device]) but excluding drugs intended to control bleeding episodes or used in the context of minor surgery (e.g., tooth extraction) or injuries (e.g., concussion) to prevent deterioration
- Systemic immunomodulators (e.g., rituximab, interferon) other than anti-retroviral therapy
- Elective surgery (excluding minor procedures such as tooth extraction, CVAD removal, or incision and drainage as well as emergency surgeries)

- Use of aPCC/PCC for short-term prophylaxis
 - Note: This criterion does not apply to the 4 weeks prior to initiation of study treatment.
- Use of other investigational drugs
- Use of anti-fibrinolytics in conjunction with aPCC/PCC or other bypassing agents (e.g., Byclot®)
- Use of concomitant prophylactic regimen with FVIII or rFVIIa

Note: This criterion does not apply to the 4 weeks prior to initiation of study treatment.

Intermittent, prophylactic doses or short-term prophylaxis (e.g., around the time of surgery), however, are permitted

If prohibited therapy is administered for any reason, it should be recorded on the eCRF. If prohibited treatment is prescribed or considered medically necessary, the Medical Monitor should be consulted to discuss any changes in the benefit/risk and determine whether the patient should continue on the study.

4.5 STUDY ASSESSMENTS

See [Appendix 1-A](#) for the schedule of assessments to be performed during the study.

4.5.1 Informed Consent Forms and Screening Log

Written informed consent for participation in the study must be obtained from the parent/legally acceptable representative and an Assent from the child when applicable before performing any study-specific screening tests or evaluations. Informed Consent Forms for enrolled patients and for patients who are not enrolled will be maintained at the study site. For adolescents (i.e., 12–17 years of age), an Informed Assent Form will be completed instead. Parents or legally authorized representatives of pediatric patients and adolescents will also complete an Informed Consent Form.

All screening evaluations must be completed within 4 weeks prior to the first dose and reviewed to confirm that patients meet all eligibility criteria before enrollment and randomization. The investigator will maintain a *detailed* record of all patients screened and to *document* eligibility or record reasons for screening failure, as applicable.

4.5.2 Medical History and Demographic Data

Medical history includes clinically significant diseases, procedures, abuse of alcohol and drugs within the past year, and medication allergies. In particular, sites should record whether the patient has any history of prior immune tolerance induction, anaphylaxis, or known thrombophilia. It should also include all medications taken within the 4 weeks prior to screening (including prescription, over-the-counter, and herbal/homeopathic remedies and therapies), or in the 24 weeks prior to screening for medications intended to treat osteopenia or osteoporosis. If the interval between screening and Week 1 is

longer than 2 weeks, all medications taken during this period should be reviewed and recorded. If imaging tests of bone health (e.g., densitometry, dual energy X-ray absorptiometry [DEXA] scan) were performed in the year prior to screening, the results should be recorded.

Additionally, the number of bleeds during the 24 weeks prior to study enrollment should be documented, as well as the number of school/work days missed and number of days hospitalized during the 24 weeks prior to study entry.

Demographic data will include age, sex, and self-reported race and ethnicity.

4.5.3 Physical Examinations

A complete physical examination should include but not necessarily be limited to the evaluation of head, eye, ear, nose, and throat and include cardiovascular, dermatological, musculoskeletal, respiratory, gastrointestinal, and neurological systems. Any abnormality identified during screening should be recorded on the General Medical History and Baseline Conditions eCRF. Subsequently, a targeted (i.e., musculoskeletal, dermatological) and/or symptom-driven examination should be conducted as noted in the schedule of assessments or as clinically indicated. New or worsened abnormalities from screening should be recorded as adverse events. A complete physical examination will be performed at screening and at least targeted physical examinations will be performed at subsequent visits.

4.5.4 Vital Signs

Vital signs will include measurement of pulse and respiratory rate, temperature (oral or tympanic), systolic and diastolic blood pressure, height, and weight and should be recorded before study drug administration. Frequency of vital sign assessments should follow the schedule of assessments but may also be taken anytime as unscheduled assessments as judged by the investigator.

4.5.5 Laboratory, Biomarker, and Other Biological Samples

Local laboratory assessments will be performed as indicated on the schedule of assessments. When study drug administration is scheduled on days of clinic visit, laboratory samples should be drawn before the administration of study drug. Laboratory assessments will include the following:

- Hematology (hemoglobin, hematocrit, platelet count, RBC count, WBC count, absolute differential count [neutrophils, eosinophils, lymphocytes, monocytes, and basophils], mean corpuscular volume, mean corpuscular hemoglobin, mean corpuscular hemoglobin concentration, and RBC distribution width)
- Serum chemistries (sodium, potassium, glucose, blood urea nitrogen, creatinine, calcium, phosphorus, magnesium, total and direct bilirubin, albumin, alanine aminotransferase, aspartate aminotransferase, and alkaline phosphatase)

- In patients who receive bypassing agents, the following local laboratory tests will be performed within 24–48 hours of initial bypassing agent use so the investigator may monitor for potential thromboembolic events and thrombotic microangiopathy:

- Platelet count
- Serum creatinine
- Lactate dehydrogenase (LDH)
- Peripheral blood smear analysis to evaluate for schistocytes

A plasma sample should also be provided for laboratory monitoring of:

- Fibrinogen
- D-dimer

For patients who require multiple doses of bypassing agents, local laboratory monitoring should be performed every 24–48 hours thereafter until 24–48 hours following the last dose of bypassing agents administered to treat a given bleed. If applicable, laboratory results should be recorded on the Unscheduled Visit eCRFs.

- Pregnancy test: All women of childbearing potential (including those who have had a tubal ligation) will have a serum pregnancy test at screening and within 7 days prior to initiation of study medication, if applicable.

Urine pregnancy tests will be performed at specified subsequent visits. If a urine pregnancy test result is positive, it must be confirmed by a serum pregnancy test.

The following samples will be sent to the Sponsor or a designee for centralized analysis:

- Plasma samples for PK analysis
- Plasma samples for immunogenicity assessment (ADA)
- Serum and plasma for PD and exploratory PD biomarker assessments (aPTT, PT, FVIII activity, and others as listed in [Appendix 2](#))
- Plasma samples for anti-FVIII antibody measurement (inhibitor titer) will be sent to the Sponsor throughout the study, with the exception of the test needed at screening for patients who do not have a documented negative inhibitor test (<0.6 BU) within 6 weeks prior to enrollment.

Please see the schedule of assessments, [Appendix 1-A](#), for detailed information. For sampling procedures, storage conditions, and shipment instructions, see the laboratory manual.

When a patient withdraws from the study, samples collected prior to the date of withdrawal may still be analyzed, unless the patient specifically requests that the samples be destroyed or local laws require destruction of the samples.

4.5.6 Electrocardiograms

ECG recordings will be obtained at study sites at specified timepoints, as outlined in the schedule of assessments (see [Appendix 1-A](#)) and may be obtained at unscheduled timepoints as indicated.

All ECG recordings must be performed using a standard high-quality, high-fidelity digital electrocardiograph machine equipped with computer-based interval measurements. Lead placement should be as consistent as possible. The following parameters will be obtained: heart rate, QT, respiratory rate, QT interval corrected using Bazett's formula, QT interval corrected using Fridericia's formula, PR and QRS, and T-and U-wave morphology. ECG recordings must be performed after the patient has been resting in a supine position for at least 10 minutes.

All ECGs are to be obtained prior to other procedures scheduled at that same time (e.g., vital sign measurements, blood draws) and should ideally not be obtained within 3 hours after any meal. Circumstances that may induce changes in heart rate, including environmental distractions (e.g., television, radio, conversation) should be avoided during the pre-ECG resting period and during ECG recording.

Any ECG changes that are deemed clinically significant by the investigator (e.g., associated with symptoms or lead to a change in study treatment or concomitant treatment, or discontinuation from study treatment), must be reported as an adverse event on the adverse event eCRF. The investigator or designee must review, sign, and date all ECG tracings. The ECG may be repeated if investigator deems it appropriate. Paper copies will be kept as part of the patient's permanent study file at the site.

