6.5 SAFETY ANALYSES

The safety analyses population will be based on all enrolled patients grouped according to the actual treatment received. For Arm C patients, all safety data reported up to the day prior to switching will be included in the "control arm" safety summaries, and all safety data reported on or after the date of switching to active treatment will be reported separately.

Safety will be assessed for Arms A, B, and C and separately for Arm D through descriptive summaries of adverse events, laboratory test results (serum chemistry and hematology, including complete blood count with differential), ECGs, vital signs, and antibodies to emicizumab and FVIII.

To evaluate the overall safety of prophylactic emicizumab compared with no prophylaxis, the incidence of adverse events will be summarized and presented by System Organ Class mapped term, appropriate thesaurus level, and toxicity grade for each treatment arm.

For clinical laboratory data, summary statistics will be presented by treatment arm. In addition, shift tables describing changes from baseline will be presented using the WHO toxicity grading scale.

Data on the effect of immunogenicity (anti-emicizumab antibodies) on safety, efficacy, and/or clinical pharmacology and pharmacokinetics will be summarized adopting standard language/terminology (Shankar et al. 2014).

Although this is an open-label study, Sponsor personnel will not have access to safety summaries by treatment arm prior to the formal reporting of the study results. HCPs at participating study sites, as well as the Sponsor's drug safety and medical monitoring staff, will have access to the treatment assignments of patients for safety monitoring purposes only.

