Appendix 1-A Schedule of Assessments

Schedule of Assessments—Arms A and B																		
	Screen-ing ^a	Wk 1	Wk 2	Wk 3	Wk 4	Wk 5	Wk 7	Wk 9	Wk 13	Wk 17	Wk 21	Wk 25	Q8W from Wk 33	Wk 49	Q12W from Wk 61	Daily/weekly ^b	Study Comp/ET ^c	Early Disc. Safety F/U Visit before Study Comp ^d
Informed consent ^e	x																	
Inclusion/exclusion criteria	x																	
Medical history and demographics ^f	x																	
Physical examination (including weight) ^g	x	x				x					x		x			x	x	
Height	x										x		x					
Vital signs ^h	x	x ^h	x	x	x	x	x	x	x	x	x ^h	x	x ^h	x		x ^h	x	
Serum pregnancy test ⁱ	x	x																
Urine pregnancy test ⁱ		x			x		x	x	x	x	x	x	x	x		x	x	
Concomitant medications ^j	x	x			x		x	x	x	x	x	x	x	x		x	x	
ECG ^k	x	x ^k			x						x					x		
Safety laboratory assessments ⁱ	x ⁱ	x	x	x	x	x	x	x	x	x	x	x	x	x		x	x	
Bleed/medication questionnaire ^l															x			
Bleed/medication data review ^l		x			x		x	x	x	x	x	x	x	x		x	x	
Adverse events ^m		x	x	x	x	x	x	x	x	x	x	x	x	x		x	x	
IMP management ⁿ		x	x	x	x	x	x	x	x	x	x	x	x	x		x		
HRQoL and health status (EQ-5D-5L) ^o		x							x			x		x		x		
Emicizumab administration ^p		x	x	x	x	x	x	x	x	x	x	x	x	x	x	x		
PK/PD/ADA assessment ^q	See Appendix 2-A for details																	
Following treatment with bypassing agents ^r	Monitoring for thromboembolic events and thrombotic microangiography ^r																	

Emicizumab—F. Hoffmann-La Roche Ltd

114/Protocol YO39309, Version 5

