Appendix 1-A (cont.) Schedule of Assessments

	Schedule of Assessments—Arm D																			Study Comp/ET ^c	Early Disc. Safety F/U Visit before Study Comp ^d
	Screen-ing ^a	Wk 1	Wk 2	Wk 3	Wk 4	Wk 5	Wk 7	Wk 9	Wk 13	Wk 17	Wk 21	Wk 25	Wk 29	Wk 33	Wk 37	Wk 41	Wk 49	Q12W from Wk 61	Daily/weekly ^b		
Informed consent ^e	x																				
Inclusion/exclusion criteria	x																				
Medical history and demographics ^f	x																				
Physical examination (including weight) ^g	x					x			x			x			x		x	x		x	x
Height	x											x					x				
Vital signs ^h	x	x	x	x	x	x	x	x	x	x	x	x	x	x	x	x	x	x	x	x	
Serum pregnancy test ⁱ	x	x																			
Urine pregnancy test ⁱ		x			x		x	x	x	x	x	x	x	x	x	x	x	x	x	x	
Concomitant medications ^j		x	x	x	x	x	x	x	x	x	x	x	x	x	x	x	x	x	x	x	
ECG ^k	x	x			x															x	
Safety laboratory assessments ⁱ	x		x		x			x	x	x	x	x	x	x	x	x	x	x	x	x	
Bleed/medication questionnaire ^l																			x	x	x
Bleed/medication data review ^s		x			x		x	x	x	x	x	x	x	x	x	x	x	x	x	x	
Adverse events ^m		x	x	x	x	x	x	x	x	x	x	x	x	x	x	x	x	x	x	x	
IMP management ⁿ		x	x	x	x	x	x	x	x	x	x	x	x	x	x	x	x	x	x	x	
Haemo-QoL-Short Form ^o	x							x			x			x		x		x		x	
Adapted Inhib-QoL ^o	x							x			x			x		x		x		x	
Emicizumab administration ^p		x	x	x	x	x	x	x	x	x	x	x	x	x	x	x	x	x	x		
PK/PD/ADA assessment ^q		See Appendix 2-A for details.																			
Following treatment with bypassing agents ^r		Monitoring for thromboembolic events and thrombotic microangiopathy ^r																			

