- ^d In the event a patient discontinues emicizumab early before the study completion, an early discontinuation safety follow-up visit should be performed 24 weeks after discontinuation of emicizumab. *If a patient enters extension phase, follow Appendix 1-B for study completion or early discontinuation safety follow up.*
- ^e Obtain written informed consent (or patient's assent and caregiver written informed consent if patient is an adolescent/pediatric) before distribution of electronic, handheld device and collection of any data. Patients will be enrolled and randomized after giving informed consent, and assent when appropriate.
- ^f Collected from patient medical records and documented on the eCRF, including information on target joint(s).
- ^g Calculation of dose based on weight is required. A complete physical examination will be performed at screening and at least a targeted physical examination will be performed at subsequent visits. Targeted physical examination of joints (for bleeds, evidence of arthropathy) and skin (for bruises, hematomas, and injection-site reactions) as clinically indicated and/or with report of new or worsening adverse event.
- ^h Body temperature (oral or tympanic), blood pressure, pulse rate, and respiratory rate only to be used to monitor hypersensitivity reactions during and after injection and not to be entered on eCRF, except at Weeks 1, 25, 49, study completion/early termination, and at the Early Discontinuation Safety Follow-up visit before study completion (i.e., 24 weeks after discontinuing emicizumab for patients in Arms A and B and at Week 73 for patients in Arm C). Weight will be measured and recorded in the eCRF at each clinic visit prior to any injections (if applicable.) Height will be measured at screening and annually.

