Appendix 1-A (cont.) Schedule of Assessments

- ⁱ Laboratory data (performed locally) include: complete blood count with differential (i.e., neutrophils, hemoglobin, platelet count), serum chemistries (i.e., sodium, potassium, glucose, blood urea nitrogen, creatinine, calcium, phosphorus, magnesium, total and direct bilirubin, albumin, alanine aminotransferase, aspartate aminotransferase, and alkaline phosphatase). Laboratory assessments completed at the screening visit do not have to be repeated at Week 1, if the period between screening and Week 1 is 5 days or less and there has been no change in health status as assessed by the investigator. Patients with childbearing potential will be required to have a negative serum pregnancy test result at screening (and within 7 days of study drug initiation, if applicable) and urine pregnancy tests performed at every clinic visit, with the exception of Weeks 2–4 and 7. Patients on Arm C will have urine pregnancy test performed at screening and before starting emicizumab (Week 25).
- ^j Concomitant medications (e.g., extra pain medication with bleed) will be asked about at the time of the monthly assessment, excluding treatments for bleeds (i.e., FVIII and other medications to treat bleeds), which will be collected on the bleeding questionnaire.
- ^k Performed locally. If screening ECG is abnormal, repeat at Week 1 (or Week 2 if screening and Week 1 occur on the same day), otherwise do not repeat. ECGs will also be performed 4–8 and 24 weeks after starting emicizumab or dose up-titration, as well as at study completion/early termination.
- ^l Reported by the patient or their caregivers and includes: start date and time, reason, type, location, and associated symptoms for joint and muscle bleeds, as well as start date and time, reason, type, and dose of each injection, excluding emicizumab.
- ^m Injection-site reaction adverse events will be collected on a separate form from the adverse event form. If there is unexpected worsening of the patient's hemophilia in terms of severity (e.g., increased number of doses of FVIII to stop bleeds compared with before study entry), frequency of bleeds, or nature at any time during the study, this should be documented as an adverse event on the Adverse Event eCRF, conveying that the underlying condition has changed by including applicable descriptors (e.g., "increased clinical severity of hemophilia").

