Appendix 1-B
Schedule of Assessments - Extension Phase

Extension Phase Schedule of Assessments — Arm A, B, C, and D				
	Extension Phase Day 1 ^a	Every 24 Weeks ^a	Extension Phase Completion/Extension Phase Early Termination ^b	Extension Phase Early Disc. Safety F/U Visit
Informed consent ^c	x			
Physical examination (including weight and height) ^d	x	x	x	x
Vital signs ^e	x	x	x	x
Concomitant medications ^f	x	x	x	x
Safety laboratory Assessments ^g	x	x	x	x
Adverse events ^h	x	x	x	x
IMP management ⁱ	x	x		
Emicizumab dispensing and administration ^j	x	x		
Following treatment with bypassing agents ^k	Monitoring for thromboembolic events and thrombotic microangiopathy			

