#### **4.7.5 Electrocardiogram**

ECG results and corresponding changes from baseline will be summarized by treatment arm and visit for QT, RR, HR, QTcB, QTcF, PR, and QRS and T- and U-wave morphology.

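### The Arm D assessment grid has no ECG at Week 25, although its own footnote requires one 24 weeks after starting emicizumab

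*Protocol*

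**What the plan says.** Section 4.5.6 of the protocol sets no ECG visits itself. It states that "ECG recordings will be obtained at study sites at specified timepoints, as outlined in the schedule of assessments" and cites Appendix 1-A; unscheduled recordings are also allowed.

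Footnote k of Appendix 1-A, attached to the ECG row, says that "ECGs will also be performed 4–8 and 24 weeks after starting emicizumab or dose up-titration, as well as at study completion/early termination". The general notes to the same appendix place the Week 25 evaluation after a full 24 weeks in the study. Section 3.1 says that ECGs follow the schedule and are the same for all patients; the only exception it names concerns PK and anti-drug antibody sampling in Arm C before the switch.

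The grid headed "Schedule of Assessments—Arms A and B" carries an ECG at the 24-week visit, as does the Arm C grid after the switch. The grid headed "Schedule of Assessments—Arm D" does not.

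For later follow-up, footnote d says: "If a patient enters extension phase, follow Appendix 1-B for study completion or early discontinuation safety follow up". The table in Appendix 1-B, "Extension Phase Schedule of Assessments — Arm A, B, C, and D", has no ECG row.

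On analysis, Protocol Section 6.5 says "Safety will be assessed for Arms A, B, and C and separately for Arm D through descriptive summaries of adverse events", and the list goes on to include ECGs. SAP 4.7.5 says that "ECG results and corresponding changes from baseline will be summarized by treatment arm and visit for QT, RR, HR, QTcB, QTcF, PR" and further parameters are reported.

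**The concern.** Site staff plan visits from the grid and may not read every footnote. If the Arm D grid is followed, children under 12 have one on-treatment ECG soon after the loading period and none at 24 weeks, where the other arms have one. Protocol 6.5 reports Arm D separately, so the gap could not be filled from other patients, and a missed 24-week recording cannot be made up later. Arm D is the study's only source of data below age 12, since Arms A to C start at 12.

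Two related points need clearing up. Footnote k asks for an ECG at study completion, but footnote d hands extension patients to a schedule without one, and the protocol does not say whether that is intended. Section 4.5.6 also lists respiratory rate among the ECG parameters, where the SAP lists RR.

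**Working it through.** No planned figure is to be reproduced here. The check compares the ECG rows with the footnote.

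**ECG marks in each Appendix 1-A grid**

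| Grid | Marks | Visits |
|---|---|---|
| Arms A and B | 5 | Screening, Week 1, Week 5, Week 25, completion/early termination |
| Arm C after switch | 4 | Week 25 (first dose), Week 29, Week 49, and a last mark read as completion/early termination |
| Arm D | 4 | Screening, Week 1, about Week 5, completion/early termination |

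For Arm C, Week 49 − Week 25 = 24 weeks on emicizumab, so the 24-week ECG is there.

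**What footnote k implies for Arm D.** Screening and Week 1 (2 marks), plus 4–8 weeks, 24 weeks and completion (3 marks), make 5. The Arm D grid has 4, so it is one short.

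**Could column displacement explain it?** In the text copy of these tables some marks sit one column to the left. The urine pregnancy row shows this: footnote i excludes Weeks 2–4 and 7, yet marks appear under Weeks 4 and 7. They belong under Weeks 5 and 9. The same correction moves the third ECG mark from Week 4 to Week 5.

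The Arms A and B and Arm D grids have the same columns up to Week 25, and Week 25 lies 6 columns after Week 5. In the Arms A and B row the fourth ECG mark is 6 cells after the third, as expected. In the Arm D row the next mark is 15 cells after the third, at the completion end of the table. The Arm D row has 21 cells for 21 columns. A one-column shift can decide between Week 4 and Week 5; it cannot produce a Week 25 mark.

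**Size.** 15 planned children × 1 omitted ECG = at most 15. The number falls with any child who stops before 24 weeks and with any site that follows the footnote; it is 0 if all sites do.

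**Completion ECG.** The notes to Appendix 1-A tie the study completion evaluation to stopping emicizumab or moving to another study. Section 3.1 describes the extension as a phase of this study, so entering it does not trigger that visit. Appendix 1-B has 9 assessment rows, none of them ECG, and its footnotes mention none. Whether footnote k's completion ECG carries over is left open, in every arm.

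**The case against.** The strongest reply is that footnotes are part of the schedule. Footnote k sits on the Arm D ECG row, so the 24-week ECG is already required and one cell merely fails to repeat it. That is correct and limits the point: the requirement exists, and the defect is that grid and footnote disagree.

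A second reply is that the tables are damaged in the text copy and a mark may have been lost. Displacement is ruled out above; outright loss is not, so the printed table should be checked. The full cell count in the row makes loss unlikely.

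Third, Section 3.1 is imperfect evidence. The physical examination rows also differ between Arm D and Arms A and B (9 marks against 7), so its statement of sameness is not kept elsewhere. Footnote k is the firmer ground.

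Fourth, the consequences are modest. ECG is not listed among the safety endpoints in Table 2, Section 5.1.2 names no ECG or QT risk, and Arm D is descriptive. The SAP follows protocol version 3 and covers Arms A to C only, so the Arm D ECG summary rests on Protocol 6.5 alone. All of this stands and keeps the point small.

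Three stronger readings are tempting but unsupported:

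- A reader might infer that a child who enters the extension has no scheduled ECG after about Week 5. That is true of the grid cells only; footnote k's 24-week ECG still applies.
- A reader might count 15 × 3 = 45 ECGs under footnote k against 15 × 1 = 15 under the grids, a loss of 30 (67%). This assumes that all 15 children enter the extension and none is up-titrated, although up-titration resets the schedule with an ECG (Appendix 2-D, footnote e). It also applies footnote k to the extension, where footnote d points elsewhere. Appendix 1-B is a reduced schedule, without PK, quality-of-life or bleed data, so leaving ECGs out may be deliberate. Patients who never enter the extension keep their completion ECG.
- A reader might infer that the SAP's RR table would be empty or hold breathing rates. Section 4.5.6 specifies machines that compute intervals and collects heart rate and both QT corrections, so RR remains available.

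**Conclusion.** The point holds as an internal contradiction. The Arm D grid omits a 24-week ECG that footnote k requires, that Section 3.1 implies, and that the other arms' grids show. Its size is one ECG per child, at most 15, if sites follow the grid and every planned child reaches 24 weeks. The result would be a separate Arm D ECG summary with no 24-week time point. This rests on the printed table having the same four marks as the text copy.

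The absent ECG in Appendix 1-B is an unclear handover between two schedules, not a demonstrated error. The respiratory rate wording is a term mismatch with no shown effect on the data. Neither the primary analysis nor any tested endpoint is affected. The correction is worth making because it is cheap and it changes what sites collect.

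**What to change.** - Reconcile the Arm D ECG row in Appendix 1-A, footnote k and Section 3.1 so that all three give the same time points. Aligning the grid with the footnote takes one table cell and adds no procedure that the protocol does not already require. If fewer ECGs are intended for Arm D, footnote k and Section 3.1 should say so and give the reason.
- State in footnote d or Appendix 1-B whether footnote k's study-completion ECG applies to patients who complete or stop in the extension. Either answer resolves the ambiguity with one sentence; an ECG row in Appendix 1-B is needed only if the answer is yes.
- Use one term for the ECG parameter in Protocol 4.5.6 and SAP 4.7.5.
- If Arm D children have already passed Week 25, establish which sites followed the grid, and report the number with a 24-week ECG alongside the Arm D summary.

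The text changes are a table cell and a few words, and fit in any routine amendment. The last item is a data-listing check.
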